13.10.5. Safety Tables

Safety: Tables					
No.	Population	GSK Standard/ Example Shell	Title	Programming Notes	Deliverable [Priority]
Adverse Events (AEs)					
3.1.	Safety	AE5B	Summary of All Adverse Events by Maximum Grade by System Organ Class and Preferred Term – Part 1	ICH E3	SAC [1], HL

Safety: Tables					
No.	Population	GSK Standard/ Example Shell	Title	Programming Notes	Deliverable [Priority]
3.2.	Safety	AE5B	Summary of All Adverse Events by Maximum Grade by System Organ Class and Preferred Term – Part 2	ICH E3	SAC [1], HL
3.3.	Safety	AE5B	Summary of All Adverse Events by Maximum Grade by System Organ Class and Preferred Term – Part 3	ICH E3	SAC [1], HL
3.4.	Safety	AE3	Summary of Common (>=5%) Adverse Events by Overall Frequency – Part 1	ICH E	SAC [1]
3.5.	Safety	AE3	Summary of Common (>=5%) Adverse Events by Overall Frequency – Part 2	ICH E	SAC [1]
3.6.	Safety	AE3	Summary of Common (>=5%) Adverse Events by Overall Frequency – Part 3	ICH E	SAC [1]
3.7.	Safety	AE5B	Summary of All Drug-Related Adverse Events by Maximum Grade by System Organ Class and Preferred Term – Part 1	ICH E3	SAC [1], HL
3.8.	Safety	AE5B	Summary of All Drug-Related Adverse Events by Maximum Grade by System Organ Class and Preferred Term – Part 2	ICH E3	SAC [1], HL
3.9.	Safety	AE5B	Summary of All Drug-Related Adverse Events by Maximum Grade by System Organ Class and Preferred Term – Part 3	ICH E3	SAC [1], HL
3.10.	Safety	AE15	Summary of Common (>=5%) Non-serious Adverse Events by System Organ Class and Preferred Term (Number of Subjects and Occurrences) – Part 1	FDAAA, EudraCT	IA [1], SAC [1]

Safety: Tables					
No.	Population	GSK Standard/ Example Shell	Title	Programming Notes	Deliverable [Priority]
3.11.	Safety	AE15	Summary of Common (>=5%) Non-serious Adverse Events by System Organ Class and Preferred Term (Number of Subjects and Occurrences) – Part 2	FDAAA, EudraCT	IA [1], SAC [1]
3.12.	Safety	AE15	Summary of Common (>=5%) Non-serious Adverse Events by System Organ Class and Preferred Term (Number of Subjects and Occurrences) – Part 3	FDAAA, EudraCT	IA [1], SAC [1]
3.13.	Safety	AE5B	Summary of Adverse Events of Special Interest by Maximum Grade by System Organ Class and Preferred Term – Part 1	Use GSK3640254 SRT spreadsheet at time of reporting to identify AESI	SAC [1]

CONFIDENTIAL

212548

Safety: Tables					
No.	Population	GSK Standard/ Example Shell	Title	Programming Notes	Deliverable [Priority]
3.14.	Safety	AE5B	Summary of Adverse Events of Special Interest by Maximum Grade by System Organ Class and Preferred Term – Part 2	Use GSK3640254 SRT spreadsheet at time of reporting to identify AESI	SAC [1]
3.15.	Safety	AE5B	Summary of Adverse Events of Special Interest by Maximum Grade by System Organ Class and Preferred Term – Part 3	Use GSK3640254 SRT spreadsheet at time of reporting to identify AESI	SAC [1]
Serious and Other Significant Adverse Events					
3.16.	Safety	AE16	Summary of Serious Adverse Events by System Organ Class and Preferred Term (Number of Subjects and Occurrences) – Part 1	FDAAA, EudraCT	SAC [1], HL
3.17.	Safety	AE16	Summary of Serious Adverse Events by System Organ Class and Preferred Term (Number of Subjects and Occurrences) – Part 2	FDAAA, EudraCT	SAC [1], HL
3.18.	Safety	AE16	Summary of Serious Adverse Events by System Organ Class and Preferred Term (Number of Subjects and Occurrences) – Part 3	FDAAA, EudraCT	SAC [1], HL

Safety: Tables					
No.	Population	GSK Standard/ Example Shell	Title	Programming Notes	Deliverable [Priority]
3.19.	Safety	AE1	Summary of Adverse Events Leading to Permanent Discontinuation of Study Treatment or Withdrawal from Study by System Organ Class and Preferred Term – Part 1	GSK Statistical Display Standard	SAC [1], HL
3.20.	Safety	AE1	Summary of Adverse Events Leading to Permanent Discontinuation of Study Treatment or Withdrawal from Study by System Organ Class and Preferred Term – Part 2	GSK Statistical Display Standard	SAC [1], HL
3.21.	Safety	AE1	Summary of Adverse Events Leading to Permanent Discontinuation of Study Treatment or Withdrawal from Study by System Organ Class and Preferred Term – Part 3	GSK Statistical Display Standard	SAC [1], HL
Laboratory: Chemistry					
3.22.	Safety	LB1	Summary of Chemistry Changes from Baseline	ICH E3, Page by Part	SAC [1], HL
3.23.	Safety	LB15A	Summary of Worst Case Chemistry Results Relative to Normal Range Post-Baseline Relative to Baseline	ICH E3	SAC [1]
Laboratory: Hematology					
3.24.	Safety	LB1	Summary of Haematology Changes from Baseline	ICH E3, Page by Part	SAC [1], HL
3.25.	Safety	LB15A	Summary of Worst Case Haematology Results Relative to Normal Range Post-Baseline Relative to Baseline	ICH E3, Page by Part	SAC [1]
Laboratory: Urinalysis					
3.26.	Safety	UR1	Summary of Worst Case Urinalysis Results Post-Baseline Relative to Baseline – Part 1	ICH E3, For discrete or character values only	SAC [1], HL
3.27.	Safety	UR1	Summary of Worst Case Urinalysis Results Post-Baseline Relative to Baseline – Part 2	ICH E3, For discrete or character values only	SAC [1], HL

Safety: Tables					
No.	Population	GSK Standard/ Example Shell	Title	Programming Notes	Deliverable [Priority]
3.28.	Safety	UR1	Summary of Worst Case Urinalysis Results Post-Baseline Relative to Baseline – Part 3	ICH E3, For discrete or character values only	SAC [1], HL
ECG					
3.29.	Safety	EG1	Summary of ECG Findings - Part 1	GSK Statistical Display Standard	SAC [1]
3.30.	Safety	EG1	Summary of ECG Findings – Part 2	GSK Statistical Display Standard	SAC [1]
3.31.	Safety	EG1	Summary of ECG Findings – Part 3	GSK Statistical Display Standard	SAC [1]
3.32.	Safety	EG10A	Summary of Maximum QTc Values Post-Baseline Relative to Baseline by Category	GSK Statistical Display Standard, ICH E14, page by part	SAC [1], HL
3.33.	Safety	EG2	Summary of Change from Baseline in ECG Values by Visit	GSK Statistical Display Standard, page by part	SAC [1]
3.34.	Safety	EG11A	Summary of Maximum Increase in QTc Values Post-Baseline Relative to Baseline by Category	GSK Statistical Display Standard, page by part	SAC [1], HL
Vital Signs					
3.35.	Safety	VS3A	Summary of Vital Sign Shifts from Baseline Relative to Potential Clinical Importance (PCI) Criteria	GSK Statistical Display Standard, page by part	SAC [1], HL

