and guided by safety data and PK stopping criteria. Post-dose safety and PK data through Day 16 from a minimum of 4 participants receiving VH3739937 are required for dose escalation in Part 1. The suitable crossover point from Part 1 to Part 2 referenced in the above text was determined once the single dose safety and preliminary PK data for the anticipated minimally effective dose was evaluated in Part 1 single ascending dose (SAD) and the maximum exposure for the MAD dose was covered by the SAD certain dose level. In Part 2, Cohorts 3 and 4, dose escalation will be determined by the VH/GSK study team and the PI and guided by the safety and PK data (minimally up to Day 29, 15 days following the Day 14 dose) from the previous dosing Cohort(s). Dose escalation from Cohort 5 will be similarly guided by safety and PK data minimally up to Day 33, 15 days following the Day 18 dose.

Based on human PK predicted from preclinical species, assuming an average bioavailability of ~14% and dose proportionality as well as predicted moderate between-participant PK variability, the highest dose to be assessed in Part 1 was anticipated to be ~640 mg QD. However, as indicated by data evaluated for Part 1 Treatment Periods through 640 mg, VH3739937 exposures are lower than predicted, therefore an additional higher dose SAD treatment period will be evaluated. This higher dose will be conducted in accordance with PK stopping criteria.

Disclosure Statement: This is a double-blind (sponsor unblinded) three-part study that includes two placebo-controlled single ascending dose cohorts (Part 1), four placebo-controlled multiple ascending dose cohorts (Part 2) and an open label RBA and FE cohort (Part 3).

Number of Participants:

Overall, approximately 76 participants will be randomly assigned to study intervention. In Part 1, approximately 18 participants will be randomized with approximately 9 participants within each of Cohort 1 and Cohort 2. Part 1 will include an additional higher dose treatment period (800 mg) evaluated in approximately 9 participants, as supported by emerging data. In Part 2, approximately 40 participants will be randomized with approximately 10 participants within each of Cohorts 3 to 6. In Part 3, approximately 18 participants will be treated to ensure that approximately 12 evaluable participants complete Cohort 7.

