The duration of dosing in Cohort 5 is to support up to 18-day dosing as an oral lead for the future SAD and MAD studies of the long acting formulation of VH3739937. This duration is to potentially allow the identification of any early drug hypersensitivity reactions (HSR) which may occur before the administration of the long acting formulation. In each escalating dose cohort, 7 participants will be randomized to receive VH3739937 and 3 participants will be randomized to receive placebo (PBO). Dose escalation in Part 2 will be determined by the VH/GSK study team and the PI based on the double-blind (sponsor-unblinded) safety and PK data (minimally up to 15 days following the last dose) from the previous dosing Cohort(s). Specifically, safety and PK data through Day 29 in Cohorts 3 and 4, and through Day 33 in Cohort 5 from a minimum of 5 participants receiving active drug will be required for dose escalation.

Part 2 of the study was initiated once the single dose safety and preliminary PK data was evaluated in the SAD and the maximum exposure for the first MAD dose in Cohort 3 was covered by the SAD certain dose level. The potential minimally effective daily dose for VH3739937 with the suspension formulation was determined by the modeling and simulation utilising data for all doses in Part 1, as 25 mg, and is anticipated to be that which is predicted to provide a steady state $C\tau \geq 0.258 \mu\text{g/mL}$ in 95% of participants.. More detailed information may be found in the IB Supplement [GlaxoSmithKline Document Number 2021 [RPS_CLIN_004025](#)].

Dose escalation in the MAD will not exceed 2-fold between cohorts 3 to 5 and will be driven by safety and PK stopping criteria (see Section [7.1.4](#)). The 500 mg dose included in the MAD Cohort 6 was determined following modelling and simulation of PK data acquired in the SAD treatment periods through to 640 mg and MAD Cohort 3. In addition, a dose will not be assessed in the MAD until the anticipated steady-state exposure (C_{\max} and $AUC(0-\tau)$ on Day 14 for Cohorts 3 and 4, on Day 18 for Cohort 5 and at Day 14 following the third QW dose in Cohort 6) for that dose have been evaluated and shown not to have met safety stopping criteria in the SAD portion of the study (Part 1).

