5.3. Lifestyle Considerations

5.3.1. Meals and Dietary Restrictions

- Refrain from consumption of red wine, Seville oranges, grapefruit or grapefruit juice, pomelos, exotic citrus fruits, grapefruit hybrids, or their fruit juices within 7 days before the start of study intervention until the end of the study.
- In Part 1 and 2, participants will refrain from water intake between 1-hour pre and 1-hour post dosing. No water intake restrictions at other times.
- All doses of VH3739937 in Part 1, Part 2, and Part 3 (Treatments A and B only) in this study will be administered in the fed state (moderate fat). The participants in Part 1, Part 2 and Part 3 (Treatments A and B) will fast for at least 9.5 hours prior to dosing and will receive a standardized moderate fat meal 25 minutes prior to dosing. Participants will eat this meal in up to 25 minutes with dose administration to occur within 5 minutes of completion of meal consumption. Participants will not receive any further food until 4 hours post-dose. The standardized moderate fat meal will contain about 600 calories with approximately 30% of them coming from fat.

- Meal times should be approximately uniform across all treatment periods. The food content of meals must be identical on serial PK sampling days. At all other times, meals will follow site usual practice.
- The participants in Part 3 (Treatment C) will be administered study intervention in the fasted state. The participants will fast overnight for at least 9.5 hours prior to dosing and until 4 hours after dosing. No water is allowed from 2 hours prior to dosing until 2 hours after dosing except for the glass of water needed to administer the study medication (e.g. 240 mL). Water is allowed ad libitum at all other times.
- In MAD Cohort 5 Day 18 only, participants will undergo biliary metabolism testing using the Enterotest or EnteroTracker for analysis of VH3739937 and its metabolites. The duodenal bile sample collected from placebo-dosed participants in this same cohort will be considered as the control sample. The string as a capsule device will be swallowed by fasted participants at approximately 2 hours after dosing on Day 18 of dosing and removed at approximately 6.5 hours post dose.
- Additional details on the Bile Sample Collection, Food Cue, EnteroTest or EnteroTrack placement, bile sample storage and shipment procedures can be found in the study reference manual (SRM).

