Treatment Assignment	
Part 1 (SAD):
 
 Participants in either Cohort 1 or Cohort 2 will be assigned to 1 of the 3 treatment sequences in a cross-over, and each participant will receive placebo once. 
  
 Cohort 1	Period 1	Period 2	Period 3	
   
 Sequence 1	Placebo	Dose 3	Dose 5	
 
 Sequence 2	Dose 1	Placebo	Dose 5	
 
 Sequence 3	Dose 1	Dose 3	Placebo	
  
 
  
 Cohort 2	Period 1	Period 2	Period 3	
   
 Sequence 1	Placebo	Dose 4	Dose 6	
 
 Sequence 2	Dose 2	Placebo	Dose 6	
 
 Sequence 3	Dose 2	Dose 4	Placebo	
  
 
 When the 800 mg dose is evaluated, 9 new participants, who were not previously exposed to any dose of VH3739937 will be enrolled in the study. Six participants randomized to receive VH3739937 and 3 participants will be randomized to receive placebo. 
Part 2 (MAD):
 
 In Cohorts 3 to 5, 10 participants per cohort (active/PBO=7/3) will receive a once-daily dose of VH3739937 or PBO for 14 days (Cohort 3 and 4) or 18 days (Cohort 5) In Cohort 6, 10 participants (active/PBO=7/3) will receive a once-weekly dose of 500 mg VH3739937 or PBO over the course of 14 days (Doses on Day 1, 8, and 15) 	Cohort 1	Period 1	Period 2	Period 3	Sequence 1	Placebo	Dose 3	Dose 5	Sequence 2	Dose 1	Placebo	Dose 5	Sequence 3	Dose 1	Dose 3	Placebo	Cohort 2	Period 1	Period 2	Period 3	Sequence 1	Placebo	Dose 4	Dose 6	Sequence 2	Dose 2	Placebo	Dose 6	Sequence 3	Dose 2	Dose 4	Placebo
Cohort 1	Period 1	Period 2	Period 3																														
Sequence 1	Placebo	Dose 3	Dose 5																														
Sequence 2	Dose 1	Placebo	Dose 5																														
Sequence 3	Dose 1	Dose 3	Placebo																														
Cohort 2	Period 1	Period 2	Period 3																														
Sequence 1	Placebo	Dose 4	Dose 6																														
Sequence 2	Dose 2	Placebo	Dose 6																														
Sequence 3	Dose 2	Dose 4	Placebo																														

Overview of Study Design and Key Features	

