5. CONSIDERATIONS FOR DATA ANALYSES AND DATA HANDLING CONVENTIONS

5.1. Study Treatment & Sub-group Display Descriptors

Treatment comparisons of relative bioavailability and food effect will be displayed as follows using the descriptors respectively:

1. (B vs. A): VH3739937 X 100 mg (single dose given as 100 mg tablet(s)) administered under moderate fat conditions (test) vs. VH3739937 X 100 mg (single dose oral suspension of VH3739937 dispersion) administered under moderate fat conditions (reference)
2. (B vs. C): VH3739937 X 100 mg (single dose given as 100 mg tablet(s)) administered under moderate fat conditions (test) vs. VH3739937 X 100 mg (single dose given as 100 mg tablet(s)) administered under fasted conditions (reference).

Treatment Group Descriptions			
RandAll NG		Data Displays for Reporting	
Code	Description	Description	Order in TLF
Part 1			
P	Placebo	SD PBO	1
D1	GSK3739937 Dose Level 1	SD 10mg	2
D2	GSK3739937 Dose Level 2	SD 30mg	3
D3	GSK3739937 Dose Level 3	SD 80mg	4
D4	GSK3739937 Dose Level 4	SD 160mg	5
D5	GSK3739937 Dose Level 5	SD 320mg	6
D6	GSK3739937 Dose Level 6	SD 640mg	7
D7	GSK3739937 Dose Level 7 800 mg	SD 800mg	8
Part 2			
RP	Placebo Repeated Dose	QD PBO	9
R1	GSK3739937 Repeat Dose Level 1	QD 25mg	10
R2	GSK3739937 Repeat Dose Level 2	QD 50mg	11
R3	GSK3739937 Repeat Dose Level 3	QD 100 mg	12
WP	Weekly Placebo	QW PBO	13
W1	GSK3739937 Weekly Repeat Dose 500 mg	QW 500mg	14
Part 3			
A	GSK3739937 PiB Fed 100 mg	PiB Fed	15
B	GSK3739937 Tablet Fed 100 mg	Tablet Fed	16
C	GSK3739937 Tablet Fasted 100 mg	Tablet Fasted	17

NOTES:

- Order represents treatments being presented in TFL, as appropriate.

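### Part 2 adverse-event tables compare 100 mg QD, where all 7 swallow a bile string, with pooled placebo (3 of 9) and 25/50 mg (none), so procedure-caused GI events can look dose-related

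*SAP*

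**What the plan says.** **Allocation.** Protocol 1.1 states: "In Part 2, approximately 40 participants will be randomized with approximately 10 participants within each of Cohorts 3 to 6". SAP 2.3 gives the split for daily dosing: "In Cohorts 3 to 5, 10 participants per cohort (active/PBO=7/3) will receive a once-daily dose of VH3739937 or PBO".

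**Placebo column.** SAP 5.1 defines one placebo group for the daily regimen, "Placebo Repeated Dose", displayed as QD PBO beside QD 25, 50 and 100 mg. Weekly placebo has its own column.

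**Procedure.** Protocol 5.3.1 states: "In MAD Cohort 5 Day 18 only, participants will undergo biliary metabolism testing using the Enterotest or EnteroTracker". Placebo participants have it too: "The duodenal bile sample collected from placebo-dosed participants in this same cohort will be considered as the control sample". Protocol 8.4 confirms that only Cohort 5 is sampled. It describes a weighted capsule on a line that reaches the duodenum and is later withdrawn.

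**Displays.** SAP 13.10.5 lists Table 3.2, "Summary of All Adverse Events by Maximum Grade by System Organ Class and Preferred Term – Part 2", and Table 3.14, "Summary of Adverse Events of Special Interest by Maximum Grade by System Organ Class and Preferred Term – Part 2". Table 3.8 repeats the layout for events judged drug-related. The programming note for Table 3.14 says only how events of special interest are identified. The notes for Tables 3.2 and 3.8 only cite ICH E3. No listed display shows placebo by cohort or separates events around the procedure.

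**Counting rules.** SAP 7.1 includes GI intolerance or toxicity among the events of special interest. SAP 13.4.2 counts events as treatment-emergent up to 22 days after the last dose. Protocol 9.4.1 tabulates relationship to study product; it has no category for relationship to a procedure.

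**The concern.** GI tolerability is one of the main safety questions of Part 2. Protocol 2.3 names GI intolerance as a major potential risk, and Protocol 2.2.1 reports a dose relationship for GI events with an earlier maturation inhibitor. A reader of Tables 3.2 and 3.14 will therefore look across 25, 50 and 100 mg for a GI trend.

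The string is an invasive GI procedure given to everyone at the top daily dose, to a third of the pooled comparator and to nobody at the lower doses. Any GI events that it causes fall in the pattern that a dose effect would produce, and the planned tables offer no means of telling the two apart. Cohort 5 also supports the planned oral lead-in to the long-acting formulation (Protocol 4.1), so a false GI signal there could affect later decisions.

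**Working it through.** **Inputs**
- 7 active and 3 placebo per cohort (Protocol 1.1; SAP 2.3).
- Four Part 2 cohorts, three of them dosed daily (SAP 2.3).
- String in Cohort 5 only, active and placebo (Protocol 5.3.1 and 8.4).
- Assumed, because the documents give neither: q, the chance that the string causes a GI event in a participant, and b, the background chance of a GI event.

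**Reproducing the plan's figure.** 4 × (7 + 3) = 40, which matches the planned Part 2 total.

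**Procedure exposure by column**

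| Column | Planned n | Swallow the string |
|---|---|---|
| QD 25 mg | 7 | 0/7 |
| QD 50 mg | 7 | 0/7 |
| QD 100 mg | 7 | 7/7 |
| QD PBO, pooled | 3 × 3 = 9 | 3/9 |

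**Expected GI incidence with no drug effect**
- 100 mg: s = b + (1 − b)q
- Pooled QD PBO: (3s + 6b)/9 = b + (1 − b)q/3
- 25 and 50 mg: b
- Excess of 100 mg over pooled placebo: (1 − b) × (2/3)q

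**Chance that 100 mg looks worst.** Take 100 mg as Binomial(7, s), pooled placebo as Binomial(3, s) plus Binomial(6, b), and 25 and 50 mg combined as Binomial(14, b). Exact summation gives the probability that the 100 mg proportion is above both of the others.

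| q | Excess, b = 0 | Chance worst, b = 0 | Excess, b = 20% | Chance worst, b = 20% |
|---|---|---|---|---|
| 10% | 6.7 points | 51% | 5.3 points | 44% |
| 20% | 13.3 points | 75% | 10.7 points | 56% |
| 30% | 20.0 points | 86% | 16.0 points | 67% |

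In participants, the excess at b = 0 is 7 × (2/3)q = 0.5, 0.9 and 1.4 of 7.

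**Within-cohort comparison.** Against the 3 Cohort 5 placebo participants, both groups have incidence s, so the expected procedure-driven difference is 0 for any q. At b = 0 and q = 20%, 100 mg shows the higher proportion 46% of the time and the lower 43%. The comparison has no systematic bias but is very imprecise.

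**Observation windows.** Treatment-emergent counting runs to Day 18 + 22 = Day 40 in Cohort 5 and to Day 14 + 22 = Day 36 in Cohorts 3 and 4. Six of the 9 pooled placebo participants have the shorter dosing and window, a small further imbalance in the same direction.

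**The case against.** **The size is assumed.** This stands. The documents give no GI rate for the string. A reader might infer that procedure events will appear as a dose signal; the documents support only that they can. Background GI events also blur the pattern, as the b = 20% columns show.

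**Table 3.8 is largely protected.** This stands. It holds only events judged drug-related, and Protocol 10.3.3 has the investigator weigh alternative causes and timing. A GI event attributed to the string stays out. A reader might infer that Table 3.8 is distorted as much as the other two, but the procedure reaches it only through misattribution.

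**Safety is descriptive, and the listings allow case review.** Partly stands. Listings 11 and 12 let a reader trace the few events involved. They do not change the summary tables, and Table 3.2 is a headline deliverable.

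**Pooling placebo is reasonable with 3 per cohort.** This stands as a reason to keep the pooled column. It is no reason to leave out the one placebo group that had the procedure.

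**Some material is unseen.** The mock shells are not in the SAP, and the event terms are kept by another compound's safety team. A footnote might already exist there. The pooling is read from the single group in SAP 5.1.

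**The tempting remedy would do harm.** A reader might infer that the dose comparison should count only Cohort 5 GI events that start before the string is swallowed. That would remove 100 mg events up to Day 40, including Days 20 to 40, while Cohorts 3 and 4 kept theirs to Day 36. With a half-life of about 90 hours (Protocol 4.1), counting would stop while exposure was still high. A cut at swallowing also needs clock times for adverse events, which SAP 13.4.2 uses only if they are collected.

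**Conclusion.** The confounding is real and follows from the plan's own allocation and display rules. Tables 3.2 and 3.14 set a column with 7/7 exposed to the procedure beside columns with 3/9, 0/7 and 0/7, and nothing listed lets a reader separate the procedure from the dose.

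Its size is not known. With no drug effect and no background events, the expected excess over pooled placebo is two-thirds of the string's GI rate. The figures assume planned cohort sizes, full uptake of the procedure, independent participants and one shared background rate.

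The documents do not support saying that a false signal is certain. They do support a low-cost display change, made before the results are tabulated, so that a Day 18 GI excess at 100 mg does not need a post hoc explanation.

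**What to change.** In SAP 13.10.5, keep the pooled QD PBO column and all treatment-emergent events in the main counts. For GI events in Tables 3.2 and 3.14, add programming notes to:
1. also show Cohort 5 placebo (n = 3) separately from Cohorts 3 and 4 placebo (n = 6);
2. add a row or flag, for Cohort 5 active and placebo, for GI events with onset on Day 18 or 19, by date, or from swallowing if event times are collected;
3. add a footnote naming the bile-string procedure, its day and who had it.

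Do not truncate the 100 mg comparison at Day 18; events from Day 20 onward stay in it. Table 3.8 needs no structural change.

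The cost is minor change to a standard display and a placebo column of 3, where one event is 33%. No new data, participants or procedures are needed, and no event leaves the counts.
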